
6 DATA CAPTURE AND PROCESSING

6.1 Data Source

6.1.1 *Medical History*

To be collected from patient charts and patient/surrogate, where applicable.

1. Demographic and admission data
2. Pertinent medical history with comorbidities and physical examination
3. Height, gender, measured body weight, calculated predicted body weight
4. Pre-hospital times and interventions
5. Time on ventilator prior to enrollment
6. High flow nasal oxygen (HFNO) and non-invasive ventilation (NIV) use for the 3 calendar days prior to meeting ARDS criteria
7. Mechanisms of Injury if the primary cause of ARDS due to trauma:
 - a. Abbreviated injury score by region
 - b. Injury severity score
 - c. Presence of hypotension on admission (SBP < 90 within 24 hours of admission)
 - d. Need for blood transfusion, as well as volume of blood and components transfused during the 1st 24 hours after injury.
 - e. Volume of crystalloid resuscitation transfused during the 1st 24 hours after injury.
 - f. Procedures performed prior to randomization
 - g. Intubated on arrival or time to intubation after admission
 - h. Base deficit (lowest level in each 24 hour period)
8. Acute or chronic renal failure and use of dialysis
9. History of lung disease
10. History of solid organ transplant
11. History of bone marrow transplant
12. COVID-19 vaccination status prior to enrollment (number, type, and date of doses)
13. Etiology of ARDS
14. Outpatient medications

6.1.2 *Baseline Assessments*

We will record the following information during the 24-hour interval preceding randomization from patient charts. If more than one value is available for this 24-hour period, we will record the value closest to the time of randomization. If no values are available from the 24 hours prior to randomization, then values will be measured post randomization but prior to initiation of study drug.

1. APACHE III Score
2. Vital signs: Heart rate, systolic and diastolic blood pressure, body temperature, mean arterial pressure, central venous pressure (if available)

3. Ventilator mode, tidal volume, FiO_2 and PEEP, inspiratory plateau pressure, and mean airway pressures. If on a pressure-targeted mode, peak pressure during inspiration will be assumed to be the plateau pressure
4. Arterial PaO_2 , PaCO_2 , pH and transcutaneous oxygen saturation and base deficit
5. Date and time of all creatinine determinations in the 96 hours prior to enrollment.
6. Frontal chest radiograph – radiographic lung injury score (# of quadrants)
7. Vasopressors or inotropes (epinephrine, norepinephrine, phenylephrine, vasopressin, dopamine $> 5 \mu\text{g}/\text{kg}/\text{min}$, dobutamine, phosphodiesterase inhibitors)
8. Suspected or known site of infection
9. Baseline platelet count and kidney/liver function tests: creatinine, total bilirubin, alanine aminotransferase. Make laboratory measurements as specified in the Clinical Protocol if not available from testing obtained as part of clinical care
10. Baseline assessments must include all data needed for the 4-point acute lung injury score, SOFA score, Ordinal Scale of Clinical Assessment (OSCI) and trauma registry index (if applicable)
11. COVID-19 test results (if applicable)

6.1.3 Assessment after Enrollment: Determination of Stable Baseline for Study Product Administration and Monitoring During and After Infusion Protocol

The following parameters will be measured and recorded every 15 minutes for the two-hour period used to establish the stable baseline prior to the study product infusion:

1. Respiratory: FiO_2 , PEEP, transcutaneous oxygen saturation; additional ventilator parameters will be recorded if clinically available.
2. Cardiovascular: Heart rate, systolic and diastolic blood pressure, vasopressor doses.

The same clinical parameters will be recorded every 15 minutes for the duration of the infusion and every hour for the next 5 hours.

An arterial blood gas will be obtained within 90 minutes prior to beginning the baseline stability period, at the end of the study product infusion (~1 hour), and 6 hours (+/- 1 hour) after the initiation of the study product infusion; additional blood gases will be recorded at 12, 18, 24, 30 and 36 hours (+/- 1 hour for all timepoints) after the initiation of study product infusion. If an arterial blood gas is collected +/- 1 hour of an indicated timepoint for clinical purposes, another arterial blood gas does not need to be collected for research.

6.1.4 Assessment after Enrollment: Reference Measurements

The following data will provide the basis for assessing protocol compliance and safety as well as between-group differences in several efficacy variables. Data for each of the variables will be recorded on the days shown in the Time-Events Schedule (**Table 2**) or until death, discharge from the ICU, or unassisted ventilation for 48 hours.

The following parameters will be measured and recorded at the time of Randomization as well as on subsequent dates using values closest in time to 8:00 A.M. on the days specified in the Time-Events Schedule (**Table 2**). The following conditions will be ensured prior to measurements: no endobronchial suctioning for 10 minutes; no invasive procedures or ventilator changes for 30 minutes. All vascular pressures will be zero-referenced to the mid-axillary line.

1. If receiving assisted ventilation, record daily up to day 7:
 - a. Tidal volume, FiO₂, PEEP, inspiratory plateau pressure, and mean airway pressures
 - b. Pressure during inspiration if on a pressure targeted mode (PSV, PCV, etc)
 - c. Arterial PaO₂, PaCO₂, pH and transcutaneous oxygen saturation
2. Fluid intake and output
3. Vital signs: Heart rate, systolic and diastolic blood pressure, body temperature, CVP
4. Modified Brussels Score data on days 0 through 14: Vasopressor use (Y/N), lowest systolic blood pressure, creatinine, bilirubin, and platelet count for the day
5. The date and value of the highest creatinine between days 15 and 28
6. Safety laboratory studies: all creatinine and bilirubin measurements will be recorded as above. Creatinine, bilirubin and ALT will be measured and recorded as safety labs on day 7 if not obtained as part of clinical care
7. Data regarding infections, including:
 - a. Surgical site and wound infections by CDC criteria
 - b. Ventilator associated or nosocomial pneumonia as diagnosed by CDC criteria
 - c. Culture-proven bacteremia
 - d. SARS-CoV-2 virus infection
8. Blood product transfusions
9. On-study procedures and surgical interventions
10. Co-enrollment in randomized clinical trials of other interventions and treatments related to SARS-CoV-2 infection
11. Inpatient medications (selected)
12. Must include all data needed for the 4-point acute lung injury score (including frontal chest radiograph), SOFA score, OSCI score and trauma registry index (if applicable)
13. D-dimer, lymphocyte count, neutrophil count, fibrinogen, ferritin and serum C-reactive protein (if applicable)
14. Date and time of specimen collection and the time of specimen processing and storage

6.1.5 Endpoint Determinations

1. Vital status at 60 days
2. Brussels Organ dysfunction failures at days 0-14
3. SOFA score at 3, 7 days
4. Oxygenation index (PaO₂/FiO₂ and mean airway pressure) at 6, 12, 18, 24, 30 and 36 hours after the initiation of study product infusion as well as on days 2, 3, and 7 if still being ventilated with positive pressure (cannot be calculated if patient is on pressure support, as the mean airway pressure is not reliable)
5. Ventilatory ratio at 6, 12, 18, 24, 30, 36 hours after the initiation of study product infusion, and on days 2, 3, 7

6. Incidence of barotrauma on days 1, 2, 3 and 7
7. Time when patient achieves pressure support ventilation with 5 cmH₂O over 5 cmH₂O positive end-expiratory pressure for 2 hours
8. Time of initiation of unassisted breathing (assuming a patient achieves 48 consecutive hours of unassisted breathing)
9. Need for re-instituting assisted or mechanical ventilation after achieving 48 consecutive hours of unassisted breathing
10. Status 48 hours after initiation of unassisted breathing
11. Need for, timing, and duration of dialysis; change in renal function as measured by creatinine
12. ICU length of stay in calendar days including ICU days after readmission to ICU
13. Hospital length of stay in calendar days
14. Discharge diagnoses and discharge disposition (home, other facility, with or without assisted ventilation)
15. WHO Ordinal Scale of Clinical Assessment at days 7, 14 and 28

6.1.6 Assessments After Hospitalization

A health status questionnaire will be conducted at 28 days, 60 days and 6 months through telephone interviews.

6.2 Case Report Form

Case report forms (CRFs) are the primary data collection instruments for the study. All data requested on the CRFs must be recorded. All missing data must be explained. If a space on the CRF is left blank because the procedure was not done or the question was not asked, write "N/D". If the item is not applicable to the individual case, write "N/A". All entries should be printed legibly in black ink. If any entry error has been made, to correct such an error draw a single straight line through the incorrect entry and enter the correct data above it. All such changes must be initialed and dated. DO NOT ERASE OR WHITE OUT ERRORS. For clarification of illegible or uncertain entries, print the clarification above the item, then initial and date it.

6.3 Data Entries and Data Quality Control

The research coordinators will transfer data to the Clinical Coordinating Center (CCC) through a secure, HIPPA compliant, web-based data collection system (www.studydata.net) developed by QuesGen, LLC. Data quality will be reviewed remotely using front-end range and logic checks at the time of data entry and back-end monitoring of data using SAS program. Patient records and case report forms will be examined on a spot check basis to evaluate the accuracy of the data entered into the database and monitor for protocol compliance. The data manager at the Clinical Coordinating Center at University of California San Francisco (UCSF) will examine the data integrity and quality on all enrolled patient with pre-defined data checklist, and issue data queries using the data management tools provided by the web-based data collection system continuously and provide structured data collection training to recruitment sites before the initiation of Phase 2b trial. The data capture system will also provide a data trace documentation which includes the history of original data entries, queries, and data revisions.

7 ENDPOINTS AND COVARIATES

7.1 Primary Study Endpoint

The primary study endpoint will assess whether an intravenous infusion of hMSCs in patients with ARDS will lead to a reduction in the severity of ARDS as measured by a decrease in the oxygenation index (OI) compared to baseline OI (prior to administration of the study product) over the first 36 hours after the initiation of study product infusion (with measurements of OI at 6, 12, 18, 24, 30 and 36 hours) (15, 16).

7.2 Secondary Endpoints

7.2.1 *Efficacy Secondary Endpoints*

We will test six categories of efficacy endpoints in this Phase 2b trial: respiratory physiology, secondary infection, systemic illness, neurologic, thromboembolic events, and biomarker profiles related to potential mechanism of hMSCs activity in ARDS.

1. **Respiratory Physiology:** Respiratory efficacy endpoints will include:

- Reduction in the 4-point acute lung injury (LIS) score after enrollment in the trial at days 1, 2, 3 and 7, or on the last day of positive pressure ventilation prior to day 7. The LIS is a composite scoring system including the $\text{PaO}_2/\text{FiO}_2$, the level of positive end-expiratory pressure, static respiratory compliance, and the quadrants of frontal chest radiograph with opacification.
- Reduction in the pulmonary dead space on days 1, 2, 3 and 7.
- Reduction in chest radiograph assessment of the extent of pulmonary edema (RALE score) at days 1, 2, 3, and 7.
- OI will be collected (as planned) also on days 2, 3, and 7 if still being ventilated with positive pressure as a secondary endpoint.
- Reduction in ventilatory ratio with measurements at 6, 12, 18, 24, 30, 36 hours, and days 2, 3 and 7.
- Incidence of barotrauma on days 1, 2, 3, and 7.
- Achieving pressure support ventilation with positive end-expiratory pressure equal to or less than 5 cm H_2O for 2 hours.
- Ventilator free-days over 7, 14 and 28 days; duration of assisted ventilation over 28 days in the survivors.

2. **Secondary Infection:** Infection efficacy endpoints will include:

- Superficial incisional/wound infections during the 14 days after enrollment.
- Deep incisional wound infections during the 14 days after enrollment.
- Organ (such as lung, liver) or space (such as peritoneum or pleural) infections during the 14 days after enrollment.
- Ventilator associated pneumonia (VAP) during the 14 days after enrollment.

3. Systemic Illness: Systemic illness efficacy endpoints will include:

- Mean SOFA score (17) at days 3, and 7.
- In hospital mortality at 14 days, 28 days, and 60 days.
- Additional prognostic value of neutrophil to lymphocyte ratio.
- Ordinal Scale for Clinical Improvement (OSCI) at days 7, 14 and 28.

To assess organ failure, we will measure serum creatinine (renal function), bilirubin (hepatic function), and platelet count (hematology) at days 0, 3, 7 and 14.

4. Neurologic: Neurocognitive efficacy endpoints will include:

- Neurocognitive function at hospital discharge by the Glasgow Outcome Score (6 points).

5. Thromboembolic: Thromboembolic safety endpoints will include:

- Incidence of thromboembolic events: Measured by ultrasound of the deep venous system or CT-angiography of the chest when clinically indicated.
- Additional prognostic value of fibrinogen at baseline.

6. Biologic: Biomarker analysis will include:

- Changes in levels of plasma, urine, and genetic biomarkers at baseline compared to 6, 24, 48, and 72 hours, including:
 - Endothelial injury (angiopoietin-2 [Ang-2])
 - Lung epithelial injury (Receptor for Advanced Glycation Endproducts [RAGE])
 - Pro-inflammatory markers (interleukin-6, interleukin-8, soluble tumor necrosis factor[sTNF-1], intercellular adhesion molecule-1 [ICAM-1], interferon gamma-induced protein-10 [IP-10], interleukin-10 [IL-10], vascular endothelial growth factor [VEGF], matrix metalloproteinase-8 [MMP-8], thrombomodulin, surfactant protein-D [SP-D], triggering receptor expressed on myeloid cells-1 [TREM-1], interleukin-18 [IL-18], plasminogen activator inhibitor-1 [PAI-1])
 - Protein C (marker of impaired coagulation)
 - Pro-resolving lipids (lipoxin A4, resolvin D₁)
 - Biomarkers that reflect the paracrine activity of the administered hMSCs (angiopoietin-1 [Ang-1], keratinocyte growth factor [KGF])
 - We will use the levels of the baseline plasma biomarkers (IL-8, Protein C, and serum bicarbonate ± vasopressor use at randomization) to classify patients as hyper- or hyper-inflammatory subphenotypes as we have described and test for higher mortality in the hyper-inflammatory group. Also, we will test for an interaction between MSC therapy and the subphenotypes for the outcomes of oxygenation index over 36 hours and 28 day mortality.
- Lung protein permeability as measured by total protein in mBAL protein at day 2; the same biomarkers will also be measured in plasma to compare MSC versus placebo treated patients.
- Measurements of urine microalbumin and urine creatinine.
- Changes in levels of plasma SARS-CoV-2 viral antigen and antibody at multiple timepoints.

- Gene expression at baseline and on days 2 and 3.

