Study Product, Dose, Route, Regimen	
The cellular product is cryopreserved for long-term storage. The cryopreserved hMSCs are formulated in CryoStor (90%) and DMSO (10%).
 
Immediately prior to administration, the product is thawed and diluted in 1:1 reconstitution media (1:1 mix of 5% human serum albumin and 10% Dextran 40). Additional reconstitution media is added to a final product volume of 300 mL.
 
Placebo: 300 mL of reconstitution media (1:1 mix of 5% human serum albumin and 10% Dextran 40).
 
Each dose of the hMSCs or placebo will be administered intravenously over approximately 60-80 minutes. All patients will receive one dose. ×
 
10 x 10⁶ cells/kg (n=60); placebo (n=60)

Primary Endpoint:	Reduction in the severity of ARDS: Change in the oxygenation index (OI) from baseline over 36 hours following the initiation of study product infusion (with measurements of OI at 6, 12, 18, 24, 30 and 36 hours).
Secondary Endpoints:	
Respiratory physiology endpoints: The 4-point acute lung injury score (LIS) at days 1, 2, 3 and 7, or on the last day of positive pressure ventilation prior to day 7; pulmonary dead space at days 1, 2, 3 and 7; chest radiograph assessment of pulmonary edema (RALE score) at days 1, 2, 3 and 7; ventilatory ratio with measurements at 6, 12, 18, 24, 30, and 36 hours, and days 2, 3, and 7; incidence of barotrauma at days 1, 2, 3 and 7; ventilator free-days over 7, 14 and 28 days; duration of assisted ventilation over 28 days in the survivors; achieving pressure support ventilation equal to 5 cm H₂O with positive end-expiratory pressure (PEEP) equal to 5 cm H₂O for 2 hours. OI will be collected (as planned) also on days 2, 3, and 7 if still being ventilated with positive pressure as a secondary endpoint.
 
Secondary Infection endpoints: Superficial incisional/wound infections, deep incisional wound infections, and organ/space infections, and ventilator associated pneumonia (all during the 14

Name of Sponsor – Investigator	[name] University of California, San Francisco
Investigational Product	Allogeneic Bone Marrow-derived Human Mesenchymal Stromal Cells (hMSCs)

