6.2 Secondary Endpoints: Phase 2b

6.2.1 Efficacy Secondary Endpoints

We will test six categories of efficacy endpoints in the Phase 2b trial: respiratory physiology, secondary infection, systemic illness, neurologic, thromboembolic events, and biomarker profiles related to potential mechanism of hMSC activity in ARDS.

1. Respiratory Physiology: Respiratory efficacy endpoints will include:

- Reduction in the 4-point acute lung injury (LIS) score after enrollment in the trial at days 1, 2, 3 and 7, or on the last day of positive pressure ventilation prior to day 7. The LIS is a composite scoring system including the $\text{PaO}_2/\text{FiO}_2$, the level of positive end-expiratory pressure, static respiratory compliance, and the quadrants of frontal chest radiograph with opacification.
- Reduction in the pulmonary dead space on days 1, 2, 3 and 7.
- Reduction in chest radiograph assessment of the extent of pulmonary edema (RALE score) at days 1, 2, 3, and 7.
- OI will be collected (as planned) also on days 2, 3, and 7 if still being ventilated with positive pressure as a secondary endpoint.
- Reduction in ventilatory ratio with measurements at 6, 12, 18, 24, 30, 36 hours, and days 2, 3 and 7.
- Incidence of barotrauma on days 1, 2, 3, and 7.
- Achieving pressure support ventilation with 5 cmH_2O and positive end-expiratory pressure equals to 5 cmH_2O for 2 hours
- Ventilator free-days over 7, 14 and 28 days; duration of assisted ventilation over 28 days in the survivors. Ventilator Free Days (VFDs) to day 28 are defined as the number of days from the time of initiating unassisted breathing to day 28 after study product

administration, assuming survival for at least two consecutive calendar days after initiating unassisted breathing and continued unassisted breathing to day 28. If a patient returns to assisted breathing and subsequently achieves unassisted breathing to day 28, VFDs will be counted from the end of the last period of assisted breathing to day 28. A period of assisted breathing lasting less than 24 hours and for the purpose of a surgical procedure will not count against the calculation of VFDs. If a patient was receiving assisted breathing at day 27 or dies prior to day 28, VFDs will be zero. Patients transferred to another hospital or other health care facility will be followed to day 28 to assess this endpoint.

2. Secondary Infection: Infection efficacy endpoints will include:

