1. At least 24 hours since enrollment in the trial
2. $\text{F}_1\text{O}_2 \leq 0.40$ and $\text{PEEP} \leq 8 \text{ cm H}_2\text{O}$ or $\text{F}_1\text{O}_2 \leq 0.50$ and $\text{PEEP} = 5 \text{ cm H}_2\text{O}$
3. Values of both PEEP and $\text{F}_1\text{O}_2 \leq$ values from previous day (comparing Reference Measurement values, section 6.3)
4. Not receiving neuromuscular blocking agents and without neuromuscular blockade
5. Patient exhibiting inspiratory efforts. If no efforts are evident at baseline, ventilator set rate will be decreased to 50% of baseline level for up to 5 minutes to detect inspiratory efforts
6. Systolic arterial pressure $\geq 90 \text{ mm Hg}$ without vasopressor support ($\leq 5 \text{ mcg/kg/min}$ dopamine or dobutamine will not be considered a vasopressor)

Spontaneous Breathing Trial Procedure and Assessment for Unassisted Breathing:

If criteria 1-6 above are met, then initiate a trial of up to 120 minutes of spontaneous breathing with $\text{F}_1\text{O}_2 < 0.5$ using any of the following approaches:

1. Pressure support (PS) $< 5 \text{ cm H}_2\text{O}$, PEEP $< 5 \text{ cm H}_2\text{O}$
2. CPAP $< 5 \text{ cm H}_2\text{O}$
3. T-piece
4. Tracheostomy mask

The clinical team may decide to change mode during spontaneous breathing (PS = 5, CPAP, tracheostomy mask, or T-piece) at any time during the spontaneous breathing trial.

Monitor for tolerance using the following:

1. $\text{SpO}_2 \geq 90\%$ and / or $\text{PaO}_2 \geq 60 \text{ mm Hg}$
2. Mean spontaneous tidal volume $\geq 4 \text{ ml/kg PBW}$ (if measured)
3. Respiratory Rate $\leq 35 / \text{min}$
4. $\text{pH} \geq 7.30$ (if measured)
5. No respiratory distress (defined as 2 or more of the following):
 - a. Heart rate $\geq 120\%$ of the 0600 rate ($\leq 5 \text{ min}$ at $> 120\%$ may be tolerated)
 - b. Marked use of accessory muscles
 - c. Abdominal paradox
 - d. Diaphoresis
 - e. Marked subjective dyspnea

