Appendix D: Ventilator Management

If any of the goals a-e are not met, revert to previous ventilator settings or to PS greater than or equal to 10 cm H₂O with Positive End-expiratory Pressure and F₁O₂ = previous settings and reassess for weaning the next morning. The patient will be reassessed for weaning (Section E2) the following day.

Decision to remove ventilatory support:

If tolerance criteria for spontaneous breathing trial (a-e above) are met for at least 30 minutes, the clinical team may decide to discontinue mechanical ventilation. However, the spontaneous breathing trial can continue for up to 120 minutes if tolerance remains in question.

3. Definition of Unassisted Breathing

1. Spontaneously breathing with face mask, nasal prong oxygen, high flow nasal oxygen, or room air, OR
2. T-tube breathing, OR
3. Tracheostomy mask breathing, OR
4. CPAP ≤ 5 without PS or IMV assistance, OR
5. Use of CPAP or BIPAP solely for sleep apnea management.

4. Definition of Extubation

1. Removal of an oral or nasotracheal tube.
2. If a patient receives a tracheostomy, the time of extubation is defined as the time when the patient achieves unassisted breathing as defined in **Section 3**.

5. Completion of Ventilator Procedures

Patients will be considered to have completed the study ventilator procedures if any of the following conditions occur:

1. Death
2. Hospital discharge
3. Alive 28 days after enrollment

If a patient requires positive pressure ventilation after a period of unassisted breathing, the study ventilator procedures will resume unless the patient was discharged from the hospital or > 28 days elapsed since enrollment.

6. Removal from the Ventilator Management Protocol

Patients may be removed from the 6 ml/kg PBW tidal volume ventilation requirement if they develop neurologic conditions where hypercapnia would be contraindicated (e.g., intracranial bleeding, GCS < 8, cerebral edema, mass effect [midline shift on CT scan], papilledema, intracranial pressure monitoring, fixed pupils).

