12.7 Analyses for Secondary Efficacy Endpoints

12.7.1 Respiratory Physiology Endpoints

The secondary endpoints, such as acute lung injury score, pulmonary dead space and RALE score, expanded oxygenation index up to 7 days and the reduction in ventilator ratios, will be analyzed by linear mix-effects regression models using the modified ITT population, in a fashion parallel to the analyses of the primary endpoint of oxygenation index. Incidence of barotrauma will be analyzed by mixed-effects logistic regression models using the modified ITT population. Counted measures, such as ventilator free days, will be analyzed using zero-inflated negative binomial models in a parallel fashion as well. Achieving pressure support and second infection endpoint will be analyzed using a logistic regression model.

The acute lung injury score (LIS), pulmonary dead space, chest radiograph assessment of pulmonary edema (RALE score) at days 0, 1, 2, 3 and 7 (5 timepoints) will be summarized in modified ITT population by allocated group.

The reduction in ventilatory ratio at 6, 12, 18, 24, 36 hours from the baseline will be summarized in modified ITT population by allocated group.

The incidence of barotrauma will be categorized as yes or not on days 1, 2, 3 and 7, and summarized by patient counts and percentages. Evidence of barotrauma includes the following:

- Pneumothorax
- Bronchopleural fistula
- Tracheobronchial fistula;
- Pneumomediastinum
- Subcutaneous emphysema
- Pneumoatocoele

Ventilator free-days by 7, 14 and 28 days will be calculated as described in *Section 8.7*. They will be summarized as median and interquartile range by allocated group, separately.

Duration of assisted ventilation over 28 days will be calculated among survivors by day 28. It will be summarized as median and interquartile range.

Achieving pressure support ventilation equal to 5 cm H₂O with positive end-expiratory pressure (PEEP) equal to 5 cm H₂O for 2 hours will be categorized as yes or not, and summarized by patient counts and percentages.

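### The pressure-support endpoint has two definitions in the SAP, and neither says how to code a patient who comes off the ventilator without 2 hours at 5 over 5

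*SAP*

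**What the plan says.** **Definition.** SAP 7.2.1 lists the endpoint as "Achieving pressure support ventilation with positive end-expiratory pressure equal to or less than 5 cm" H2O, held for 2 hours, and gives no pressure-support level. SAP 12.7.1 opens its version with "Achieving pressure support ventilation equal to 5 cm" H2O and adds PEEP equal to 5 cm H2O. The protocol agrees with SAP 12.7.1: the synopsis has "achieving pressure support ventilation equal to 5 cm" H2O with PEEP of 5, and section 6.2.1 has pressure support of 5 and "positive end-expiratory pressure equals to 5" cm H2O. Item 7 of Protocol 10.5 and item 7 of SAP 6.1.5 collect the time at which 5 over 5 for 2 hours is reached.

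**Analysis.** SAP 12.7.1 says the endpoint "for 2 hours will be categorized as yes or not, and summarized by patient counts and percentages", and that "Achieving pressure support and second infection endpoint will be analyzed using a logistic regression model".

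**Weaning rules.** Protocol Appendix D, section 2, allows a spontaneous breathing trial of up to 120 minutes by pressure support, CPAP, T-piece or tracheostomy mask. "The clinical team may decide to change mode during spontaneous breathing (PS = 5, CPAP, tracheostomy mask, or T-piece) at any time" during the trial. Once the tolerance criteria "are met for at least 30 minutes, the clinical team may decide to discontinue mechanical ventilation". The trial may run on to 120 minutes if tolerance is still in doubt.

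**Not stated.** No section gives the time window for this endpoint, the coding of a patient liberated without 2 hours at 5 over 5, or the coding of a patient who dies first. SAP 9 allows no imputation unless the SAP specifies it, and none is specified here.

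**The concern.** There are two defects, and the second matters more.

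First, the SAP carries two live definitions. A patient with 2 hours at pressure support 10 and PEEP 5 meets the SAP 7.2.1 text but not the SAP 12.7.1 text.

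Second, the version to be analysed is a ventilator-setting milestone that the trial's own weaning rules allow a recovering patient to skip. A patient who passes a T-piece trial, or is extubated after 30 minutes of tolerance, may never record 2 hours at 5 over 5. Under a literal yes/not rule that patient joins the patients who died or remained ventilated. If sites or the analyst instead leave the field blank, the patient leaves the logistic model because of a good outcome. Either way the result depends on the route of weaning as well as on recovery, and the choice between the two codings is left until data are in hand.

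**Working it through.** The documents state no rate, effect or power for this endpoint, so there is no planned figure to reproduce. The check has two parts: how the text classifies specific patients, and an illustration on assumed rates.

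**1. Classification under the current text**

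| Patient | SAP 7.2.1 | SAP 12.7.1, literal |
|---|---|---|
| 2 h at pressure support 5, PEEP 5 | yes | yes |
| 2 h at pressure support 10, PEEP 5 only | yes | not |
| 30 min at 5 over 5, then extubated | not | not |
| Weaned by T-piece, CPAP or tracheostomy mask, never 2 h at 5 over 5 | not | not |
| Died on full support | not | not |
| 2 h at 5 over 5, later changed to T-piece | yes | yes |

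Rows 3 and 4 are recovered patients placed with row 5. Row 6 shows that a mode change alone does no harm if the 2 hours were already recorded.

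**2. Illustration (all rates assumed)**

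Inputs from the documents: 60 per arm (SAP 10) and two-sided 5% (SAP 12.5). Assumed: true liberation p in each arm, and c, the share of liberated patients whose course includes 2 hours at 5 over 5. For simplicity nobody else reaches the milestone.

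Observed success = c × p.

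Power = Φ[(d − 1.96·se0)/se1], where d is the difference, se0 = √(p̄(1−p̄)·2/60) and se1 = √([p1(1−p1)+p2(1−p2)]/60).

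Worked case, 60% v 80%: p̄ = 0.70, se0 = 0.0837, se1 = 0.0816; (0.20 − 1.96 × 0.0837)/0.0816 = 0.44, so power is 67%.

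*Same c in both arms:*

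| True placebo v hMSC | c = 1 | c = 0.7 | c = 0.5 |
|---|---|---|---|
| 50% v 70% | power 61% | 35% v 49%, power 34% | 25% v 35%, power 22% |
| 60% v 80% | power 67% | 42% v 56%, power 33% | 30% v 40%, power 21% |

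The difference goes from 20 points to 14 (0.7 × 20) or 10 (0.5 × 20). The direction does not change.

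*Different c by arm:* for 60% v 80% with placebo c = 0.5, the observed difference is zero when hMSC c = 0.5 × 0.60/0.80 = 0.375. At hMSC c = 0.3 the observed rates are 30% v 24%, a reversal. With equal true liberation of 60% and c = 0.7 placebo v 0.5 hMSC, the analysis shows 42% v 30%.

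**3. The missing-data reading**

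Take 60% v 80% with c = 0.5 and set bypass patients to missing. Placebo: 30% yes, 30% missing, so 30/70 = 43%. hMSC: 40% yes, 40% missing, so 40/60 = 67%. The same patients give 30% v 40% under one coding and 43% v 67% under the other.

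**The case against.** A reader might infer that the plan expressly counts early extubation as failure. It does not. Failure coding comes from reading yes/not literally, and a site could record such patients as missing or not applicable. That is fair, but the missing-data reading removes recovered patients, so it replaces one problem with another.

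A reader might also infer that the fastest recoveries are generally coded as failures. The documents do not show this. Pressure support is the first-listed trial mode, the 30 minutes is a permitted minimum, and with no time window any 2-hour spell at 5 over 5 counts, whenever it occurs.

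A claim that the endpoint will change sign is not supported either. Reversal needs bypass to differ by arm. Site investigators and coordinators are blinded to assignment (SAP 12.3), so clinician preference for a weaning route should balance. A difference would have to come through the treatment itself, for example by shortening breathing trials. That is possible, but nothing in the documents quantifies it.

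On the definitions, SAP 7.2.1 stands alone against five other places, and Appendix D sets a minimum PEEP of 5, so the difference between PEEP at most 5 and PEEP equal to 5 is small. The missing pressure-support level is the substantive part.

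Finally, liberation is credited elsewhere, through ventilator-free days (SAP 8.9) and the ordinal scale (SAP 8.7), and SAP 12.5 calls secondary endpoints supportive and exploratory. This limits the consequence but does not make the endpoint interpretable as written.

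**Conclusion.** The point holds in limited form. SAP 7.2.1 conflicts with every other statement of the endpoint and should be brought into line. The analysed yes/not rule, read literally, groups a patient liberated without 2 hours at 5 over 5 with patients who died or stayed ventilated, and no rule on coding, death or time window prevents this.

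The expected effect, if bypass is similar in the two arms, is attenuation. With assumed bypass of 30% to 50%, a true 20-point difference appears as 14 to 10 points. Reversal is conditional on bypass differing by arm. All these sizes rest on assumed liberation rates and bypass shares, because the documents supply neither. The primary endpoint is not touched. The change is worth making before database lock, but it is not critical to the trial's main conclusion.

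**What to change.** Change the analysis coding only; weaning care stays as it is.

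1. Replace the SAP 7.2.1 text with the definition used elsewhere: pressure support 5 with PEEP 5 for 2 hours.
2. State a time window, for example day 28 after study product administration, to match ventilator-free days.
3. Code as success the first of 2 hours at 5 over 5 or unassisted breathing as defined in Appendix D, section 3 (which section 4 also uses to time extubation in a patient with a tracheostomy).
4. Code death before either event as failure.
5. Use the same wording in Protocol 6.2.1 and SAP 7.2.1 and 12.7.1.

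Cost: a wording change. The time of 5 over 5 and the time of unassisted breathing are already collected (items 7 and 8 of Protocol 10.5 and of SAP 6.1.5). Item 8 records the latter for patients who achieve 48 consecutive hours, so the rule should say whether that condition applies. The downside is some overlap with ventilator-free days. If the sponsor wants to keep the milestone unmixed, reporting the count of patients liberated without it, by arm, beside the coded result would show how much the coding matters.
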